### 3.4. Study Procedures

Protocol-specific evaluations and their schedule in detail during the whole study period are summarized in [Table 1](#). in the protocol synopsis section. [Figure 1](#) shows the overview of the study scheme.

**Figure 1. Study Scheme**

- 1) Post-treatment follow-up will be done at 4 weeks (± 7 days) after the end of treatment (EOT).
- 2) Survival follow-up will be done at 8 weeks (± 7 days) interval after the Post-treatment follow-up visit.

Survival follow-ups will continue until the death of the subject or till the study closure.

### 3.4.1. Screening Visit

Upon signing on the informed consent form, the screening period will start. Screening should be completed within 28 days before the date of randomization. Within this period, following procedures are to be carried out. Any procedures or assessments associated with the study should be initiated only after obtaining the written informed consent from potential subjects. If procedures within the 28-day window were performed as part of standard of care prior to consent, those evaluations may be used as screening period results.

- Informed consent
- Collection of demographic information
- Collection of medical history
- Collection of GC history
- Collection of previous/concomitant medication information
- Assessment of adverse events

 In Japan, when the patient is under 20 years old, informed consent will be obtained from both the patient and the legal guardian.

 Medical history within 1 year (within 3 years for cancers) from signing on the ICF should be collected. Medical history includes clinically significant past and current diagnosis including surgical procedures. Any surgical procedures done for treatment of GC will be collected separately regardless when those were carried out.

 Full history of GC including date of initial diagnosis, primary location ( $\geq 5$  cm below GEJ) vs. GEJ), stage, and metastatic information should be collected.

 Any medications administered within 28 days from signing the ICF and current medications should be collected. Medications for treatment of GC will be collected separately regardless of when those were administered.

 Any untoward medical occurrence in a patient who has signed the informed consent form will be collected as an adverse event.

The following should be completed within 14 days before the baseline visit. These data except vital signs, which will be measured again in the baseline visit, will be used as baseline data for determination of eligibility of subjects in the study.

- Measurement of height
- Physical examination
- Measurement of vital signs including weight

- Assessment of ECOG performance score
- 12-lead ECG
- Hematology, blood chemistry, serological test, coagulation test and urinalysis
- Pregnancy test
- CT/MRI for GC evaluation
- Biopsy for GC evaluation
- Collection of concomitant medication information
- Assessment of adverse event
- Eligibility review by the registration center

 Please refer to [5.3.2](#) for specific item of each test panel.

 This will be ordered only for women of child-bearing potential (serum or urine) including women who have not been post-menopausal for at least 1 year prior to Screening visit.

 Tumor will be assessed based on CT (or PET-CT) scan or MRI. The same method should be used for the assessment of tumor response throughout the study.

 If a diagnosis cannot be made with CT (or PET-CT)/MRI due to atypical radiological appearance, primary or metastatic tumor biopsy is recommended. Histopathologic examination of the biopsy specimen should be assessed by an expert pathologist.

 Among the screened patients, the registration center will review those fulfilling the criteria in [Section 3.2.1](#), not meeting any of the criteria in [Section 3.2.2](#) and judged to be appropriate for the study.

### 3.4.2. Baseline Visit (Day 1 in Cycle 1)

Randomized subjects will receive the assigned investigational product as instructed. The following procedures are carried out at this visit.

- Physical examination
- Measurement of vital signs including weight
- Assessment of ECOG performance score
- 12-lead ECG (Before IP administration)
- Chest X-ray, pregnancy test (serum or urine), biopsy
- Collection of concomitant medication information
- Randomization
- Completion of patient reported outcome (EORTC QLQ-C30, EORTC QLQ-STO22, EQ-5D-5L)

- Pharmacodynamic (PD) marker test
- Dispense of investigational product
- Administration of investigational product
- Blood sampling for Cycle 1 Day 1 PK
- 12-lead ECG (Approximately 4 hours after IP administration and corresponding to PK sampling)
- Assessment of adverse events

 Only done when clinically indicated. The following countries require a pregnancy test at the beginning of each treatment cycle for the applicable subjects: Germany, Romania, and Poland.

If a randomized subject is found not to meet any of the eligibility criteria before the first administration of the investigational product, the subject will not be started on the study treatment and will be withdrawn from the study. Subjects who are randomized but never receive the investigational product or subjects who are withdrawn from the study before randomization will not be allowed to re-consent.

### 3.4.3. Treatment Visits After Baseline

A treatment cycle is composed of 28 days (4 weeks) and the study treatment will be continued until the death of the subject or discontinuation of the study treatment due to disease progression, intolerable toxicity or subject's withdrawal of consent. Subjects are required to visit the investigational site every 2 weeks ( $\pm$  3 days) till the death of the subject or discontinuation of the study treatment due to disease progression, intolerable toxicity or subject's withdrawal of consent. The following procedures are carried out at each treatment visit after baseline.

- Physical examination
- Measurement of vital signs including weight
- Assessment of ECOG performance score
- Assessment of adverse event
- Collection of concomitant medication information
- Chest X-ray, pregnancy test (serum or urine), biopsy
- 12-lead ECG and Pharmacodynamic (PD) marker test
- Blood sampling for PK (See [Section 5.4.4](#))
- Hematology, blood chemistry, coagulation test and urinalysis
- Completion of patient reported outcome (EORTC QLQ-C30, EORTC QLQ-STO22, and EQ-5D-5L)

- CT/MRI
- Dispense of investigational product at the first day of every cycle (as long as the study treatment is continued)

 Only done when clinically indicated. Biopsies are carried out based on the investigator's discretion, but it should be considered in case of growth or change in the enhancement pattern identified during follow-up. Histopathologic examination of the biopsy specimen should be assessed by an expert pathologist. The following countries require a pregnancy test at the beginning of each treatment cycle for the applicable subjects: Germany, Romania, and Poland.

 Measured at the first day of every cycle (4 weeks interval) prior to dosing. In addition, a 12-lead ECG should be performed approximately 4 hours after IP administration on Day 15 of Cycle 1 corresponding to the Cmax PK blood draw timepoint.

 Measured approximately every 8 weeks at the end of every other cycle from Baseline

#### 3.4.4. End of Treatment (EOT) Visit/Discontinuation

Subjects who discontinue study treatment (see [Section 6.2](#)) or subjects permanently withdrawn from the study are required to make this visit within 7 days from their final administration of the investigational product. Following procedures are carried out at this visit.

- Physical examination
- Measurement of vital signs including weight
- Assessment of ECOG performance score
- Assessment of adverse event
- Collection of concomitant medication information
- Chest X-ray, pregnancy test (serum or urine), biopsy
- 12-lead ECG
- Hematology, blood chemistry, coagulation test and urinalysis
- Pharmacodynamic (PD) marker test
- CT/MRI
- Completion of patient reported outcome (EORTC QLQ-C30, EORTC QLQ-STO22, EQ-5D-5L)

 Only done when clinically indicated. Biopsies are carried out based on the investigator's discretion but it should be considered in case of growth or change in

the enhancement pattern identified during follow-up. Histopathologic examination of the biopsy specimen should be assessed by an expert pathologist. The following countries require a pregnancy test at the end of treatment visit for applicable subjects: Germany, Romania, and Poland.

 If CT/MRI is performed within 4 weeks prior to EOT or disease progression is clearly confirmed by previous CT/MRI, tumor evaluation is not required at EOT.

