- 10) Additional pregnancy test may be performed if required by local health authorities. Additional pregnancy test is required at the beginning every treatment cycle, and at EOT visit for Germany and Romania. Additional pregnancy test is required at the beginning of every treatment cycle, at EOT visit, and at post-treatment follow-up visit for Poland.
- 11) Serological tests to be performed locally include HIV antibody (if HIV antibody result is positive, HIV-1 antibody and HIV-2 antibody should be conducted), HBs antigen, and HCV antibody.
- 12) Subjects will complete two questionnaires; EORTC-QLQ-30 with EORTC QLQ-STO22 and EQ-5D-5L at baseline and then approximately every 4 weeks typically either at the end of the cycle or at the beginning of the next cycle.
- 13) Tumor will be assessed based on chest, abdominal and pelvic CT (or PET-CT) scan or MRI approximately every 8 weeks at the end of every other cycle. The same method should be used for the assessment of tumor response throughout the study. RECIST Guideline Version 1.1 will be used to assess tumor response. CT (or PET-CT) scan/MRIs after Baseline are allowed to perform within 7 days prior to the planned visit date. Scans to confirm progression of disease or for other reasons not per schedule as determined by the investigator may be performed when needed.
- 14) If a diagnosis cannot be made with chest, abdominal and pelvic CT (or PET-CT)/MRI due to atypical radiological appearance, primary or metastatic biopsy is recommended. Subsequent biopsies are carried out based on the investigator's discretion but it should be considered in case of growth or change in the enhancement pattern identified during follow-up. Histopathologic examination of the biopsy specimen should be assessed by an expert pathologist.

- 15) Adverse events will be documented for any untoward medical occurrence in a patient from the time they sign the informed consent form and until study completion per the Study Schedule.
- 16) Any medications administered within 28 days prior to signing the ICF and current medications should be collected. Medications for treatment of GC will be collected separately regardless when those were administered.
- 17) PD markers include vascular endothelial growth factor (VEGF), sVEGFR-1, sVEGFR2 and sVEGFR3.

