#### 3.4.5. Post-Treatment Follow-Up Visit

For the purpose of safety follow-up, a post-treatment visit should be made at 28 days ( $\pm$  7 days) after the end of treatment visit. The following procedures are carried out at this visit.

- Physical examination
- Measurement of vital signs including weight
- Assessment of ECOG performance score
- 12-lead ECG
- Hematology, blood chemistry, coagulation test and urinalysis
- Assessment of adverse event
- Collection of concomitant medication information
- Chest X-ray, pregnancy test (serum or urine)

 Only done when clinically indicated. A pregnancy test for applicable subjects is required at post-treatment follow up visit for Poland.

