### 5.3. Safety Assessment

#### 5.3.1. Adverse Event

Assessments will be made on the adverse events (AEs) including any sign, symptom, disease or illness that occurred newly or if present at baseline, worsened in a subject and may impair the well-being of the subject. Clinical laboratory findings and any other findings from the diagnostic procedures that are considered clinically significant (e.g. requiring unscheduled diagnostic procedures or treatment modalities or resulting in discontinuation of the study) will also be included in the AE assessment.

AEs will be collected and evaluated at each visit after informed consent is signed until 28 calendar days after the last administration of the investigational product. Any AEs that emerged following administration of IP will be evaluated in comparison to the baseline level of AEs determined at screening.

See [Section 7](#) for detailed information on **SAFETY REPORT** of this study.

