### 6.2. Criteria for Treatment Discontinuation

Subjects may voluntarily withdraw their consent from the study or the investigator may terminate a subject's participation if the investigator judges that the subject can no longer fully comply with the study requirements or if any of the study procedures are deemed potentially harmful to the subject.

If any of the following criteria is met during the treatment period, the study treatment will be discontinued.

1. Subject withdraws his/her consent.
2. The development of disease progression is confirmed according to the RECIST guideline (version 1.1) that makes it inappropriate to continue with study treatment according to the investigator's discretion or consent for continued treatment beyond RECIST confirmed disease progression is not obtained. (see [Section 6.3](#))
3. Clinical symptoms determined to be due to disease progression that makes it inappropriate to continue with study treatment according to the investigator's discretion or consent for continued treatment beyond clinical symptoms that are determined to be due to disease progression is not obtained. (see Section 6.3)
4. Onset of CTCAE grade  $\geq 3$  hypertension for which a causal relationship to the investigational product cannot be ruled out. (However, the judgment on whether or not to continue the treatment will be made by the investigator.)
5. Not having received a dose of the investigational product within the past consecutive 3 weeks for specific reasons, such as the onset of a treatment related adverse event.
6. Treatment with prohibited concomitant medication of sufficient dose and duration to confound the study results or to make continuation or restarting of treatment within 3 weeks unsafe for the patient.

7. Intolerable toxicity even after 2 dose reductions.
8. Confirmed positive pregnancy test.
9. The subject is lost to follow-up.
10. The subject is dead.
11. The investigator determines that continuation of study treatment is not appropriate.

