Laboratory tests will continue with other study evaluations as described in the subsequent cycle study schedule to adequately ensure subject safety and further evaluations to ensure the subjects safety and continued benefit may be performed at the investigator's discretion.

After the decision to end study treatment permanently, an end of treatment (EOT) examination will be performed (at completion/discontinuation) and the subject will proceed to the post-treatment follow-up and survival follow-up. However, subjects in either treatment group will be withdrawn from the study if they meet any of the following criteria:

1. Subject withdraws his/her consent on the follow-up period.
2. Subject is lost to follow-up.

Post-treatment follow-up can be carried out before withdrawal if the subject agrees to it. Data that have already been collected on withdrawn subjects will be retained and used for analysis but no new data will be collected after withdrawal. When subjects withdraw from the study, they will be asked whether the study center can continue to contact them or family members for survival status only. If this consent is withdrawn, publicly accessible records may be used for documentation of death.

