#### **6.4. Handling Early Withdrawals**

In any case of early withdrawal from the study, the date and reason should be recorded in the subject's eCRF and source documents. If the reason for early withdrawal was an AE, the outcome of the AE should be reported according to Section 7.2 and 7.3. All subjects who have received at least one dose of IP should complete all tests scheduled for the EOT wherever possible.

Screening numbers and randomization numbers, once allocated, cannot be reused. Any new subject will always receive new subject numbers (screening number and randomization number).

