### 7.3. Serious Adverse Event Reporting

All SAE must be reported to the sponsor without delay from the time of investigator's acknowledgement on the event, whether or not the SAE has a causal relationship to the investigational product. The investigator is responsible for informing the IRB/IEC of the SAE, as per local requirements. If a non-serious AE becomes serious, this and other relevant follow-up information must also be provided to the sponsor without delay, whether or not it has a causal relationship to the investigational product. All SAE will be recorded in the eCRF. The site should fax or e-mail the SAE Report Form within 24 hours from the time of discovery of the SAE with as much information as possible to the sponsor.

During the extension period, new SAE should only be reported for subjects who are taking apatinib and have not completed Post-treatment Follow-up visit.

The SAE form should have the following information:

- Study title, protocol number, and sponsor name
- Reporter's name, investigator's name, and contact number
- Site name, site number, and subject's identification code (subject's study number)
- SAE name, start and stop dates of the event
- Causality to the investigational product, action taken in regard to investigational product, and treatments (any procedures or medications given) to manage the SAE, and the outcome of the event

If the site obtains additional information regarding the event after submitting the Initial SAE Report Form, the site should prepare a Follow-up SAE Report Form and send it to

the sponsor through fax or e-mail. Only new or corrected information should be added to the Follow-up SAE Report Form, along with identifying information regarding the subject and the event. All AE other than SAE, will be reported on the AE page of the eCRF.

The contact information for SAE reporting is as follows:

Main address:

- Name: LSK Global PS, PV department
- Email: [REDACTED]
- Fax Number: [REDACTED]

Sub address for Japan patients only (cc):

- Name: Department of Pharmacovigilance, Mediscience Planning Inc.
- Email: [REDACTED]
- Fax: [REDACTED]

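### The 7-day End of Treatment rule cannot be met after a 3-week dose hold, and the protocol gives two different end points for adverse event collection

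*Protocol*

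**What the plan says.** **EOT visit.** Protocol 3.4.4 covers everyone who stops study treatment under Section 6.2 and everyone permanently withdrawn; they are "required to make this visit within 7 days from their final administration of the investigational product". Item 5 of Section 6.2 stops treatment for "Not having received a dose of the investigational product within the past consecutive 3 weeks". Section 6.3 says: "After the decision to end study treatment permanently, an end of treatment (EOT) examination will be performed". It gives no interval. Section 6.4 adds that all subjects who took at least one dose "should complete all tests scheduled for the EOT wherever possible".

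**AE collection.** Section 5.3.1 collects AEs from consent "until 28 calendar days after the last administration of the investigational product". Section 3.4.5 states that "a post-treatment visit should be made at 28 days" (± 7 days), counted from the EOT visit, and lists AE assessment among its procedures. Table 1 marks AEs at that visit but not at survival follow-up, and footnote 15 documents AEs "until study completion per the Study Schedule".

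**Analysis.** Protocol 7.1.1 and SAP 5.9.2 define a treatment-emergent AE (TEAE) identically: it runs from the first dose to the final subject visit. Neither says which visit that is. SAP 8.2 limits the AE tables to TEAEs, and SAP 8.2.1 tests incidence between arms.

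**SAEs after the End of Study (EOS) date.** Section 7.3 says that in the extension period "new SAE should only be reported for subjects who are taking apatinib and have not completed Post-treatment Follow-up visit". Section 11.1 gathers SAEs after the EOS date until 28 days after the last dose.

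**The concern.** Two rules are wrong as written.

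The first is a deadline that one of the protocol's own stopping criteria makes impossible. This is a foreseeable route: Section 4.4 withholds drug for Grade III or IV related toxicity for up to 3 weeks, and a subject who does not recover in that time is the natural candidate for item 5. Each such subject produces a deviation that no site can avoid.

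The second is a pair of end points counted from different origins: the last dose in 5.3.1, the EOT visit in 3.4.5 and Table 1. Sites that follow different sections will record different late events. Because the AE tables hold only TEAEs, and the analysis cannot restore an event that was never recorded, the choice of section decides whether a late event is counted.

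**Working it through.** The plan states no figure for this point, so there is none to reproduce. The check is calendar arithmetic, with the last dose as day 0 and E as the day of the EOT visit.

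**Inputs.** EOT due by day 7 (3.4.4); EOT visit window ± 7 days (Table 1; SAP Table 8); item 5 needs 3 weeks without a dose (6.2); post-treatment visit at E + 28 ± 7 (3.4.5); AE collection limit day 28 (5.3.1).

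**1. Can the EOT rule be met under item 5?**
- Earliest day on which item 5 is met: 3 × 7 = 21.
- Deadline: day 7, or 7 + 7 = 14 if the visit window is added.
- Shortfall: 21 − 7 = 14 days, or 21 − 14 = 7 days with the window. The rule cannot be met either way.
- Scope: this applies only when the hold ends in permanent discontinuation. A subject who resumes dosing gets a new last-dose date.

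**2. Where does the last AE visit fall relative to day 28?**

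| Case | E | Earliest | Nominal | Latest | Relative to day 28 |
|---|---|---|---|---|---|
| Ordinary stop | 0–7 | 0 + 28 − 7 = 21 | 28–35 | 7 + 28 + 7 = 42 | −7 to +14 days |
| Stop after a 21-day hold | ≥ 21 | 21 + 28 − 7 = 42 | ≥ 49 | no upper limit given | +14 days or more |

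If the EOT window is added to an ordinary stop, E reaches 14 and the latest visit is 14 + 28 + 7 = day 49.

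**3. What this does to an event.**
- Held subject, AE starting on day 40, post-treatment visit on day 49: outside collection under 5.3.1. It is collected under Table 1, and is a TEAE if the final subject visit means the post-treatment visit.
- Ordinary stop, visit on day 21, AE starting on day 25: inside the 5.3.1 limit, but after the last scheduled AE visit, and not a TEAE on the same reading.

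Neither rule contains the other, and the conflict does not need a hold.

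**4. Rough size of the disputed interval.** The documents give no late AE rate. Assume L = 0.1–0.2 AEs of a given type per month and ignore death. The chance that at least one starts between day 28 and a visit on day v is 1 − exp(−L × (v − 28)/30.44):

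| v | L = 0.1 | L = 0.2 |
|---|---|---|
| 35 | 2.3% | 4.5% |
| 42 | 4.5% | 8.8% |
| 49 | 6.7% | 12.9% |

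These are chances per subject still alive and seen. They overstate the change in incidence, because some of these subjects will already have had the same event on treatment.

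**The case against.** The best defence is that most of this is handled elsewhere. Section 3.1 asks for evaluation at reasonable intervals during dose interruptions, including AE and laboratory follow-up. Section 3.4.3 keeps two-weekly visits going until discontinuation, and Section 6.4 keeps the EOT tests. On AEs, Table 1, footnote 15, Section 3.4.5 and both TEAE definitions point the same way, so the sentence in 5.3.1 is the outlier. What sites do in practice may depend on separate eCRF entry guidance that is not available here. All of this stands and limits the consequence. It does not make the 7-day rule achievable, and it does not tell a site reading 5.3.1 to carry on past day 28.

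A reader might also infer more than the documents support:
- **That EOT data are lost.** Section 6.4 points to a late visit, not a missing one.
- **That 6.3 sets a rival EOT clock.** It says only that the examination follows the decision, gives no interval, and sits in the section on treatment beyond progression.
- **That 8.3.7 is a competing TEAE definition because it has no end.** Section 8.3 calls itself an outline and leaves detail to the SAP, whose definition matches 7.1.1.
- **That the SAE mismatch affects the main comparison.** It concerns the period after EOS. For the main study 7.3 requires all SAEs and states no cut-off, and Section 8.3.9 has extension data summarised descriptively under a separate plan.
- **That the between-arm AE tests are materially biased.** That would need the number of hold-related stops in each arm, which the documents do not give.

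**Conclusion.** Minor, but wrong as written on two counts. The EOT deadline is unachievable for subjects stopped under item 5, by at least 14 days (7 with the visit window). AE collection has two end points that can differ in either direction for an ordinary stop, and by 14 days or more after a 21-day hold. The two TEAE definitions agree with each other, so the fault lies mainly upstream, in what sites record, together with the undefined final visit.

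The expected effect on between-arm AE comparisons is small and cannot be quantified from the documents; the percentages for the disputed interval rest on assumed AE rates. No efficacy endpoint is affected. The day counts rest only on protocol timings, except that EOT after a hold is taken to occur no earlier than the day item 5 is met.

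**What to change.** 1. **Protocol 3.4.4:** EOT within 7 days of the last dose or of the decision to discontinue, whichever is later.
2. **Protocol 5.3.1 and Table 1 footnote 15:** collect AEs through the later of day 28 after the last dose and the post-treatment visit, with a contact at day 28 if the visit falls earlier.
3. **Protocol 7.3 and 11.1:** use that same end point for SAEs.
4. **Protocol 7.1.1 and SAP 5.9.2:** replace the undefined final visit with that same end point. Do not cut the TEAE window to day 28: that would narrow two definitions that agree and drop events the plan now counts.

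The cost is wording in the two documents and an occasional day-28 contact. No table needs restructuring.

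A separate, optional improvement is to show events per patient-month beside the crude incidence in SAP 8.2.1, since time on drug may differ between arms. Event counts are already planned there and treatment duration in SAP 8.1, so the cost is about one extra column.
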